(80 per arm) that have been enrolled and have had an opportunity to be followed for the tumor assessment scheduled at week 24. This futility analysis will be based on Bayesian methods. The talimogene laherparepvec plus pembrolizumab arm is considered to be futile if the posterior probability that at least 6% absolute increase for iORR (at least 10% for iDCR) from the pembrolizumab is < 0.65 (< 0.75 for iDCR). A DMC will be responsible to review interim safety and non-binding futility analyses for iORR and iDCR. The DMC is also responsible to review the results from the primary analysis of PFS by blinded independent central review using modified RECIST 1.1 and all interim OS analyses performed by an external independent biostatistics group. At the time of PFS primary analysis, an interim OS efficacy analysis will be performed by the external biostatistics group and reviewed by the DMC. **The second interim OS analysis is planned after 282 events have occurred.** If OS is not declared statistically significant at the second interim analysis, a non-binding futility analysis will be performed. However, if 282 OS events are observed prior to the event goal for the primary PFS, then the first OS interim will be the event-driven (ie, 282 events) and a PFS interim will be conducted with all PFS events at the time of the 282 OS events interim analysis. In this case, the second OS interim analysis will be performed at the PFS primary analysis with all OS events. **The third interim OS analysis for efficacy is planned after 315 events have occurred.** Refer to Section 10.4.1.4 for additional information.

Section: 3.5.2, End of Study, Primary Completion, Paragraph 1

Delete:

Primary Completion: The primary completion date is defined as the date when the last subject is assessed or receives an intervention for the final collection of data for the primary endpoint(s), ~~for the purposes of conducting the primary analysis, whether the study concluded as planned in the protocol or was terminated early.~~

Section: 3.5.2, End of Study, Primary Completion, Paragraph 2

Add:

The primary completion date is the date when data for the primary endpoint(s) are last collected for the purpose of conducting the primary analysis.

Approved

Section: 4.1.1.1, Inclusion Criteria for Phase 1b and Phase 3, Criterion #104

Add:

Disease stage **defined as one of the following (per the seventh edition of the American Joint Committee on Cancer [AJCC] Cancer Staging Manual):** Subject with unresectable stage IIIB, IIIC, IVM1a, IVM1b, or IVM1c melanoma

Section: 7.1, Schedule of Assessments, Table 6, footnote “r”

Replace:

r Blood for PK of pembrolizumab: Pre-dose trough will be collected at week 0 (ie, pembrolizumab cycle 1), week 3 (ie, pembrolizumab cycle 2), week 12 (ie, pembrolizumab cycle 5), week 27 (ie, pembrolizumab cycle 9), week 39 (ie, pembrolizumab cycle 13) every 12 weeks (4 cycles) thereafter, at safety follow-up visit (30 [+7] days after discontinuation of study treatment), and again 3 months after study discontinuation or up until the subject starts new anticancer therapy, whichever occurs first. Every effort should be taken to collect samples at 30 days and 3 months after end of pembrolizumab treatment. All trough samples should be drawn within 24 hours before infusion of pembrolizumab. Pembrolizumab PK sample collection and analyses in phase 3 may be discontinued if ongoing PK results from this study continue to be consistent with existing PK data from other pembrolizumab melanoma clinical trials.

With:

r Blood for PK of pembrolizumab: Pre-dose trough and post-dose peak PK samples will be collected at week 0 (ie, pembrolizumab cycle 1). Pre-dose trough samples only will be collected on day 1 of week 3 (ie, pembrolizumab cycle 2), week 12 (ie, pembrolizumab cycle 5), week 27 (ie, pembrolizumab cycle 9), week 39 (ie, pembrolizumab cycle 13) every 12 weeks (4 cycles) thereafter, at safety follow-up visit (30 [+7] days after discontinuation of study treatment), and again 3 months after study discontinuation or up until the subject starts new anticancer therapy, whichever occurs first. Every effort should be taken to collect samples at 30 days and 3 months after end of pembrolizumab treatment. All trough samples should be drawn within 24 hours before infusion of pembrolizumab. The peak sample should be drawn within 30 minutes after the end of the infusion. Pembrolizumab PK sample collection and analyses in phase 3 may be discontinued if ongoing PK results from this study continue to be consistent with existing PK data from other pembrolizumab melanoma clinical trials.

Approved

Section: 10.1.1.3, [Exploratory Endpoints](#), bullet 5

Replace:

- HSU estimates derived via EQ-5D-3L at each assessment in phase 3 and post-progression.

With:

- **Changes in HSU estimates derived via EQ-5D-3L**

Section: 10.1.1.3, [Exploratory Endpoints](#), bullet 11 (new)

Add:

- **Response rates (partial, complete, partial or complete) and maximum decrease in lesion size, separately for visceral, injected, and uninjected non-visceral lesions.**

Section: 10.1.2, [Analysis Sets, PRO Population](#)

Replace:

PRO Analysis Sets

PRO analysis set will include subset of subjects in the Full Analysis Set who had received at least one dose of study therapy and had at least one PRO assessment.

With:

PRO Population

The PRO population includes the subset of the subjects in the full analysis set who had received at least 1 dose of study therapy and had at least 1 PRO assessment. A PRO assessment will be defined as completed if at least 1 subscale/domain can be calculated from the questionnaire. Patient reported outcome populations will be defined separately for each questionnaire (EORTC QLQ-C30 and EQ-5D-3L) and for the secondary endpoint of EORTC QLQ-C30 GHS/QoL.

Section: 10.1.3, [Covariates and Subgroups](#), Paragraph 2

Delete:

The following baseline covariates and randomization stratification factors may be used to examine all-efficacy in subgroups or in multivariate analyses:

Section: 10.1.3, Covariates and Subgroups, Paragraph 2, bullets 10, 11, and 14

Replace:

- The sum of longest, or shortest for nodal, diameters of target lesions (SLD)
- Pre-randomization PD-L1 status (positive, negative, indeterminant/unknown)
- Pre-randomization of BRAF^{V600} mutation: yes vs no

With:

- The sum of longest, or shortest for nodal, diameters of target lesions (SLD) **determined by blinded independent central review (will be dichotomized based on median)**
- **Baseline** PD-L1 status (positive **vs not positive**)
- **Baseline** of BRAF^{V600} mutation: yes vs no **vs missing/unknown**

Section: 10.2.2, Sample Size Considerations for Phase 3, Paragraph 2

Replace:

The overall Type I error for the dual primary endpoints is 2-sided 0.05. The event goal for PFS to achieve 90% power at 2-sided 0.005 is 407 and that for OS to achieve 90% power at a 2-sided 0.045 is 346 after taking into account the group sequential interim OS analyses. The OS event goal is not adjusted for the non-binding OS futility assessment at the second OS interim analysis. The sample size is 660 (ie, 330 per arm) based on an estimate of 346 death events occurring within 5 years (60 months) with approximately 48% of subjects censored. Assuming a non-uniform subject accrual rate for which 50% of cumulative enrollment is accrued at 2/3 of expected total enrollment period (Lachin and Foulkes, 1986), and exponential distributions for loss to follow up for PFS and OS with an annual rate of 5% for OS and 10% for PFS, Table 9 displays estimated timing of analysis based on 2 scenarios of enrollment rates:

With:

The overall Type I error for the dual primary endpoints is 2-sided 0.05. The event goal for PFS to achieve 90% power at 2-sided 0.005 is 407 and that for OS to achieve 90% power at a 2-sided 0.045 is 346 after taking into account the group-sequential interim OS analyses. The OS event goal is not adjusted for the non-binding OS futility assessment at the second OS interim analysis. The sample size is 660 (ie, 330 per arm) based on an estimate of 346 death events occurring within 5 years (60 months) with approximately 48% of subjects censored. Assuming a non-uniform subject accrual rate for which 50% of cumulative enrollment is accrued at 2/3 of expected total enrollment period (Lachin and Foulkes, 1986), and exponential distributions for loss to follow up for PFS

and OS with an annual rate of 5% for OS and 10% for PFS, Table 9 displays estimated timing of analysis based on **the actual** enrollment rate:

Section: 10.2.2, Sample Size Considerations for Phase 3, Table 9

Replace:

Table 9. Timing of Primary Analysis for PFS (at 407 events) and OS (at 346 events)

Average Enrollment Rate	Enrollment Duration (month)	PFS PA DCO (month)	OS Events (% event goal) at PFS PA DCO	OS PA DCO (month)
20/month	33	44	240 (69%)	62
33/month	20	33	222 (64%)	53

DCO = data cutoff at event goal; OS = overall survival; PA = primary analysis; PFS₁ = progression free survival per blinded independent central review using modified RECIST 1.1. N = 660

With:

Table 9. Timing of Primary Analysis for PFS (at 407 events) and OS (at 346 events)

Enrollment Duration (month)	PFS PA DCO (month)	OS Events (% event goal) at PFS PA DCO	OS PA DCO (month)
26	48	252 (73%)	75

DCO = data cutoff at event goal; OS = overall survival; PA = primary analysis; PFS₁ = progression free survival per blinded independent central review using modified RECIST 1.1.

[REDACTED]

Section: 10.2.2, Sample Size Considerations for Phase 3, Table 10, footnote a

Add:

[REDACTED]

Section: 10.4.1.4, Interim Efficacy and Futility Analysis (Phase 3), Paragraphs 1 and 2

Replace:

There are 4 planned analysis time points for hypothesis testing, including primary and/or interim analyses of the 5 hypotheses (H): H₁, associated with OS; H₂, PFS by blinded independent central review assessed modified RECIST 1.1; H₃, iPFS by blinded independent central review assessed modified irRC-RECIST; H₄, iCRR by blinded independent central review assessed modified irRC-RECIST; and H₅, OS subgroup

excluding IVM1c (Table 10). The analysis times are defined by the following event-driven time points with the DMC responsible for Analyses #1 and #2.

1. PFS primary analysis at 407 events (DMC).
2. OS interim analysis at 282 events (including a futility analysis) (DMC).
3. OS primary analysis at 346 events.
4. OS subgroup primary analysis at earlier of 208 events in subgroup or 5 years minimum follow-up.

Note that there is no sequential order in these 4 analysis times (with the exception that Analysis #2 is before Analysis #3). Each analysis time may also include interim or primary analyses for the other endpoints. Endpoints to be analyzed, and the type of analysis (ie, interim or primary), are presented in Table 11 and are dependent on which hypotheses have been rejected. For example, testing for iCRR and iPFS at an analysis time point will be conditional upon previously rejecting either H_1 or H_2 . O'Brien-Fleming group sequential boundaries based on the Lan-DeMets approach (O'Brien and Fleming, 1979) will be used for testing endpoints with interim analyses. Multiple testing procedures will utilize the graphic-based Maurer-Bretz approach (Section 10.5).

With:

There are **5** planned analysis time points for hypothesis testing, including primary and/or interim analyses of the 5 hypotheses (H): H_1 , associated with OS; H_2 , PFS by blinded independent central review assessed modified RECIST 1.1; H_3 , iPFS by blinded independent central review assessed modified irRC-RECIST; H_4 , iCRR by blinded independent central review assessed modified irRC-RECIST; and H_5 , OS subgroup excluding IVM1c (Table 10). The analysis times are defined by the following event-driven time points with the DMC responsible for Analyses #1, #2, and #3.

1. **OS interim analysis and PFS primary analysis at 407 PFS events (DMC).**
2. OS interim analysis at 282 events (including a futility analysis) (DMC).
3. **OS interim analysis at 315 events (DMC).**
4. OS primary analysis at 346 events.
5. OS subgroup primary analysis at earlier of 208 events in subgroup or 5 years minimum follow-up.

Note that there is no sequential order in these **5** analysis times (with the exception that Analysis #2 is before Analysis #3, **and Analysis #3 before Analysis #4**). Each analysis time may also include interim or primary analyses for the other endpoints. Endpoints to

be analyzed, and the type of analysis (ie, interim or primary), are presented in Table 11 and are dependent on which hypotheses have been rejected. For example, testing for iCRR and iPFS at an analysis time point will be conditional upon previously rejecting either H_1 or H_2 . O'Brien-Fleming group sequential boundaries based on the Lan-DeMets approach (O'Brien and Fleming, 1979) will be used for testing endpoints with interim analyses. Multiple testing procedures will utilize the graphic-based Maurer-Bretz approach (Section 10.5).

Section: 10.4.1.4, Interim Efficacy and Futility Analysis (Phase 3), Paragraph 3, bullets 3, 6, and 7

Replace:

3. At each of the 4 planned analysis times, it will be considered an interim analysis of iCRR and iPFS, rather than the primary analysis, if the maximum information has not been reached for the respective endpoint at that time. For example, if H_3 is tested in an analysis that includes fewer than 256 iPFS events, then it will be an interim analysis of iPFS that includes all observed events; otherwise, it will be the primary analysis with all iPFS times censored after the date of the 256th event. If all randomized subjects do not have at least 36 weeks follow-up in an analysis, then it will be an interim analysis for iCRR only including those subjects with at least 36 weeks follow-up; otherwise, it will be the primary analysis and include all randomized subjects. With the exception of PFS, the hypothesis for an endpoint may be re-tested after its primary analysis using its primary analysis data if alpha is subsequently propagated to it from the rejection of another hypothesis.
6. The OS hypothesis (H_1) will be tested at Analyses #1-3 with all (Analysis #1) or required number (Analysis #2 and Analysis #3) of events in the absence of its prior rejection (or futility at Analysis #2).
7. The OS subgroup hypothesis (H_5) will be tested at the first and all subsequent analysis times when alpha can be propagated to it from the rejection of H_1 or H_2 followed by H_3 and/or H_4 . All OS events in the subgroup at the end of 5 years follow-up will be used if 208 events have not been observed. If H_1 is not rejected by Analysis #3, it will be tested again using events at Analysis #3 if alpha can be propagated from the rejection of H_5 at Analysis #4.

With:

3. At each of the **5** planned analysis times, it will be considered an interim analysis of iCRR and iPFS, rather than the primary analysis, if the maximum information has not been reached for the respective endpoint at that time. For example, if H_3 is tested in an analysis that includes fewer than 256 iPFS events, then it will be an interim analysis of iPFS that includes all observed events; otherwise, it will be the primary analysis with all iPFS times censored after the date of the 256th event. If all randomized subjects do not have at least 36 weeks follow-up in an analysis, then it will be an interim analysis for iCRR only including those subjects with at least 36 weeks follow-up; otherwise, it will be the primary analysis and include all randomized subjects. With the exception of PFS, the hypothesis for an endpoint may be re-tested after its primary analysis using its primary analysis data if alpha is subsequently propagated to it from the rejection of another hypothesis.

6. The OS hypothesis (H_1) will be tested at Analyses #1-4 with all (Analysis #1) or required number (Analysis #2, Analysis #3, **and Analysis #4**) of events in the absence of its prior rejection (or futility at Analysis #2).
7. The OS subgroup hypothesis (H_5) will be tested at the first and all subsequent analysis times when alpha can be propagated to it from the rejection of H_1 or H_2 followed by H_3 and/or H_4 . All OS events in the subgroup at the end of 5 years follow-up will be used if 208 events have not been observed. If H_1 is not rejected by Analysis #4, it will be tested again using events at Analysis #4 if alpha can be propagated from the rejection of H_5 at Analysis #5.

Section: 10.4.1.4, Interim Efficacy and Futility Analysis (Phase 3), Paragraph 4 and Table 11

Replace:

Table 11 illustrates possible hypothesis tests at the 4 planned analyses.

Table 11. Study Analyses and Possible Hypothesis Tests

Analysis	Timing	Hypothesis Tested (Analysis Type)				
		H_1 (OS)	H_2 (PFS)	H_3 (iPFS)	H_4 (iCRR)	H_5 (OS subgroup)
#1	407 PFS events	(IA)	(PA)	If reject H_1 or H_2 (IA if < 256 events)	If reject H_1 or H_2 (IA if includes fewer than all randomized)	If reject H_2 and either H_3 or H_4 , or reject H_1 and either H_3 or H_4 (IA if < 208 events)
#2	282 OS events	(IA)	n/a (IA if Analysis #2 is performed first)	If reject H_1 or H_2 (PA on first 256 events)	If reject H_1 or H_2 (PA if includes all randomized)	If reject H_2 and either H_3 or H_4 , or reject H_1 and either H_3 or H_4 (IA if < 208 events)
#3	346 OS events	(PA)	n/a	See Analysis #2 above	See Analysis #2 above	See Analysis #2 above
#4	Earlier of 208 OS events in subgroup or 5 years minimum follow-up	If reject H_2 previously and H_5 (PA at first 346 events)	n/a	See Analysis #2 above	See Analysis #2 above	See Analysis #2 above (PA)

Approved

With:

Table 11 illustrates possible hypothesis tests at the 5 planned analyses.

Table 11. Study Analyses and Possible Hypothesis Tests

Analysis	Timing	Hypothesis Tested (Analysis Type)				
		H ₁ (OS)	H ₂ (PFS)	H ₃ (iPFS)	H ₄ (iCRR)	H ₅ (OS subgroup)
#1	407 PFS events	(IA)	(PA)	If reject H ₁ or H ₂ (IA if < 256 events)	If reject H ₁ or H ₂ (IA if includes fewer than all random-ized)	If reject H ₂ and either H ₃ or H ₄ , or reject H ₁ and either H ₃ or H ₄ (IA if < 208 events)
#2	282 OS events	(IA)	n/a (IA if Analysis #2 is performed first)	If reject H ₁ or H ₂ (PA on first 256 events)	If reject H ₁ or H ₂ (PA if includes all random-ized)	If reject H ₂ and either H ₃ or H ₄ , or reject H ₁ and either H ₃ or H ₄ (IA if < 208 events)
#3	315 OS events	(IA)	n/a	If reject H ₁ or H ₂ (PA on first 256 events)	If reject H ₁ or H ₂ (PA if includes all randomized)	If reject H ₂ and either H ₃ or H ₄ , or reject H ₁ and either H ₃ or H ₄ (IA if < 208 events)
#4	346 OS events	(PA)	n/a	See Analysis #2 and #3 above	See Analysis #2 and #3 above	See Analysis #2 and #3 above
#5	Earlier of 208 OS events in subgroup or 5 years minimum follow-up	If reject H ₂ previously and H ₅ (PA at first 346 events)	n/a	See Analysis #2 and #3 above	See Analysis #2 and #3 above	See Analysis #2 and #3 above (PA)

Approved

Section: 10.4.1.4, Futility Analysis for OS

Delete:

At the 282 OS events interim analysis (ie, Analysis #2), if hypothesis H1 is not rejected, then an OS futility analysis will be evaluated by the DMC. The interim OS futility analysis will be non binding and define futility as a conditional power < 10% assuming a constant treatment effect (Denne, 2001); the corresponding OS futility boundary is 0.89, assuming a constant HR = 0.70. OS futility will also be evaluated by the DMC considering a possible non constant treatment effect that increases over time (eg, a 2 interval model with a cutpoint between 4 8 months and constant treatment effect in each interval, where the second interval has a larger effect than the first one). To limit the probability of futility < 0.02, the futility boundary for the observed HR at 282 OS events analysis will be 0.93. Guidelines for this possible late effect will be provided in the DMC charter amendment. Operating characteristics of the primary analysis of PFS and sequential tests of OS are shown in Table 12 based on the OS events expected at Analysis #1 ~~based on 2 enrollment scenarios shown in Table 9.~~

Approved

Section: 10.4.1, Futility Analysis for OS, Table 12

Replace:

Table 12 Analysis Timing, Nominal Significance Levels, and Boundary Properties by Average Enrollment

Average enrollment	Analysis	Data cut-off (mon)	Endpoint (scenario)	Event (% goal)	Efficacy nominal 2-sided α	Prob. Futile ^b			Efficacy HR	Power total
						Futile HR ^b	H ₀	H ₁		
20/month	PFS PA	44	PFS	407 (100)	0.0050				0.76	90%
	OS IA ₁	44	OS (PFS-)	240 (69) ^a	0.0123				0.72	60%
			OS (PFS+)		0.0143				0.73	62%
	OS IA ₂	50	OS (PFS-)	282 (82)	0.0194	0.89	84%	2%	0.76	76%
			OS (PFS+)		0.0219	0.89	83%	2%	0.76	77%
	OS PA	62	OS (PFS-)	346 (100)	0.0376				0.80	90%
			OS (PFS+)		0.0416				0.80	91%
	33/month	PFS PA	33	PFS	407 (100)	0.0050				0.76
OS IA ₁		33	OS (PFS-)	222 (64) ^a	0.0088				0.70	52%
			OS (PFS+)		0.0103				0.71	54%
OS IA ₂		41	OS (PFS-)	282 (82)	0.0203	0.89	84%	2%	0.76	76%
			OS (PFS+)		0.0230	0.89	83%	2%	0.76	77%
OS PA		53	OS (PFS-)	346 (100)	0.0377				0.80	90%
			OS (PFS+)		0.0417				0.80	91%

N = 660

IA = interim analysis; H₀ = null hypothesis; H₁ = alternative hypothesis; HR = hazard ratio; OS = overall survival; PFS = progression free survival; PA = primary analysis.

O'Brien-Fleming spending α for OS; futility if conditional power < 10%; H₀: HR = 1 and H₁: HR = 0.67 (PFS) and 0.70 (OS). Testing OS at an overall 2-sided 0.045 if PFS is not significant at 2-sided 0.005 (eg, PFS-); testing OS at 0.05 when all other null hypotheses are rejected (eg, PFS+).

Approved

With:

Table 12 Analysis Timing, Nominal Significance Levels, and Boundary Properties

Analysis	Data cut-off (mon)	Endpoint (scenario)	Event (% goal)	Efficacy nominal 2-sided α	Futile HR ^b	Prob. Futile ^b		Efficacy HR	Power total
						H ₀	H ₁		
PFS PA	48	PFS	407 (100)	0.0050				0.76	90%
OS IA ₁	48	OS (PFS-)	252 (73)^a	0.0150				0.74	66%
		OS (PFS+)		0.0173				0.74	67%
OS IA ₂	52	OS (PFS-)	282 (82)	0.0187	0.89	84%	2%	0.76	76%
		OS (PFS+)		0.0212	0.89	83%	2%	0.76	77%
OS IA₃	61	OS (PFS-)	315 (91)	0.0261				0.78	84%
		OS (PFS+)		0.0292				0.78	85%
OS PA	75	OS (PFS-)	346 (100)	0.0336				0.80	90%
		OS (PFS+)		0.0372				0.80	90%

IA = interim analysis; H₀ = null hypothesis; H₁ = alternative hypothesis; HR = hazard ratio; OS = overall survival; PFS = progression free survival; PA = primary analysis. O'Brien-Fleming spending α for OS; futility if conditional power < 10%; H₀: HR = 1 and H₁: HR = 0.67 (PFS) and 0.70 (OS). Testing OS at an overall 2-sided 0.045 if PFS is not significant at 2-sided 0.005 (eg, PFS-); testing OS at 0.05 when all other null hypotheses are rejected (eg, PFS+).

Approved

Section: 10.5.5, Patient Reported Outcome Endpoints and Analyses

Replace:

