Complete Response (iCR):	Disappearance of all lesions (whether measurable or not and whether baseline or new) and confirmation by a repeat, consecutive assessment no less than 4 weeks (28 days) from the date first documented. Any pathological lymph nodes (whether target or non-target) must have reduction in short axis to <10 mm.
Partial Response (iPR):	Decrease in tumor burden ^a ≥ 30% relative to baseline confirmed by a consecutive assessment at least 4 weeks (28 days) after first documentation
Progressive Disease (iPD):	Increase in tumor burden ^a ≥ 20 % and at least 5 mm absolute increase relative to nadir (minimum recorded tumor burden) confirmation by a repeat, consecutive assessment no less than 4 weeks (28 days) from the date first documented iPD.
Stable Disease (iSD):	Neither sufficient shrinkage to qualify for iCR or iPR nor sufficient increase to qualify for iPD.
Unevaluable (iUE):	Any lesion present at baseline or a new measurable lesion which was not assessed or was unable to be evaluated leading to an inability to determine the status of that particular tumor for that time point. Exception: when iPD is documented based on a partial assessment.

Page 1 of 2

Footnotes defined on next page of table

Approved

Table 15. Definition of Measurable Tumor Response (Baseline Target and New, Measurable Lesions)

Not Applicable (NA)	No target lesions were identified at baseline
Not Done (ND)	Radiographic image, photographic image or clinical measurement were not performed at this time point to evaluate the response of measurable lesions

Page 2 of 2

^a Tumor Burden = sum of diameter of target lesions + sum of diameter of up to 10 (maximum 5 per organ) new, measurable lesions. Diameters used:

- For nodal disease, shortest axis
- For non-nodal disease, longest diameters

Table 16. Matrix for Determining the Overall Response at Each Assessment Point

Measurable Response		Non-measurable Response	Overall Response
Target and new, measurable lesions (tumor burden) ^a , %	Non-target	New, non-measurable lesions	Using modified irRC-RECIST
↓100 ^e	Absent/NA ^d	Absent	iCR ^b
↓100	Present/ND/iUE	Any	iPR ^b
↓100	Unequivocal progression	Any	iPR ^b
↓≥ 30	Absent/Present/NA ^d /ND/iUE	Any	iPR ^b
↓≥ 30	Unequivocal progression	Any	iPR ^b
↓< 30 to ↑< 20	Absent/Present/NA ^d /ND/iUE	Any	iSD
↓< 30 to ↑< 20	Unequivocal progression	Any	iSD
↑≥ 20 ^f	Any	Any	iPD ^b
iUE	Any	Any	iUE
ND	Any	Any	iUE
NA ^c	Any	Any	iUE

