iCR = complete response (per modified irRC-RECIST); iPR = partial response (per modified irRC-RECIST); iSD = stable disease (per modified irRC-RECIST); iPD = progressive disease (per modified irRC-RECIST); iUE = unevaluable (per modified irRC-RECIST); ND = not done; NA = not applicable.

^a Decrease disease relative to baseline, including new measurable lesions only (> 10 mm).

^b iCR or iPR progression should be confirmed by a second, consecutive assessment at least 4 weeks (28 days) apart. Rapid clinical deterioration is an exception for confirming initial iPD.

^c No target lesions identified at baseline. When a patient has only nonmeasurable disease (ie, no target lesions identified at baseline) the response will be unevaluable.

^d No non-target lesions identified at baseline.

^e Disappearance of all non-lymph node lesions and all lymph nodes < 10 mm in short axis would also be iCR even if lymph node measurements prevent 100% tumor burden reduction.

^f In addition to relative increase of ≥ 20%, the tumor burden must also demonstrate an absolute increase of ≥ 5 mm from nadir for iPD. If the tumor burden does not demonstrate ≥ 5 mm increase from nadir but tumor burden is increased ≥ 20% from the nadir, response should be recorded as iSD.

Determination of best overall response is based on changes in total tumor burden from the baseline (nadir, for iPD) tumor assessment, regardless of any initial increase in baseline lesions or the appearance of new lesions.

Approved

Subjects are considered to have iPR or iSD even if new lesions were present, as long as they met the respective thresholds of response as described in [Table 16](#).

A best overall response of iSD requires a visit response of iSD or better no earlier than **84** days after the date of enrollment; otherwise the overall response will be unevaluable (iUE).

Confirmation of Response (iCR or iPR):

To be assigned a status of iCR or iPR changes in tumor measurements must be confirmed by consecutive repeat assessments performed no less than 4 weeks (28 days) after the criteria for response are first met.

In some circumstances it may be difficult to distinguish residual disease from normal tissue. When the evaluation of iCR depends on this determination, it is recommended that the residual lesion be investigated (ie, biopsy) to confirm the iCR status.

Confirmation of Disease Progression:

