iBOR of complete response (iCR), partial response (iPR), stable disease (iSD), progressive disease (iPD) or unevaluable (iUE) will be derived per modified irRC-RECIST based on investigator assessment and BICR assessment, respectively. Overall visit response assessments occurring **on or** after the start of the first subsequent anticancer therapy, including complete or partial removal/reduction of any target lesion which contained melanoma on pathology evaluation or pathology results were unknown, will not be included. **The timepoint responses after initial confirmed iPD will not be used to derive BOR.** Confirmation of iCR, iPR, and iPD is required as noted in the individual definitions for iCR, iPR and iPD per modified irRC-RECIST (refer to protocol Appendix F). For the derivation of iBOR, the overall visit response will be considered iSD if it is an unconfirmed iCR or iPR, and iUE if it is either iSD earlier than 84 days after the date of randomization or an unconfirmed iPD when confirmation of iPD is required (ie, initial iPD without clinical instability). As indicated in [Table 2](#), iBOR is defined as the best overall visit response in the following order: iCR, iPR, iSD, iPD, or iUE.

Table 2. Matrix of Determining iBOR per Modified irRC-RECIST

Visit Overall Response Sequence	Examples	Best Overall Response	Specifications
* , iCR, iCR, *	iPR, iCR, iCR iCR, iCR, iPD	iCR	A confirmatory iCR must be at least 4 weeks (28 days) later; a subsequent iCR within 28 days will not be valid for confirmation and will be ignored; the iCR will also not be confirmed if there is a subsequent iPR/iSD/iPD at any time prior to the next iCR.
* , iPR, iPR, * * , iPR, iCR/iPR, non-iCR, *	iPR, iPR, iPD iPR, iCR, iPD iCR, iPR, iPD	iPR	Criteria for iBOR=iCR not met. A confirmatory iPR/iCR must be no less than 4 weeks (28 days) later; a subsequent iPR/iCR within 28 days will not be valid for confirmation and will be ignored; the iPR will also not be confirmed if there is a subsequent iSD/iPD at any time prior to the next iPR/iCR.
* , iSD, * * , iCR, non-iPR/iCR, * * , iPR, non-iPR/iCR, *	iCR iPD, iCR iPR iPD, iPR, iSD iSD iPD, iSD, iPD	iSD	Criteria for iBOR=iCR or iPR not met. iSD must be ≥ 84 days from date of randomization; however, this is not required for an unconfirmed iCR/iPR.

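### Table 16 footnote f of Protocol Appendix F records a visit ≥ 20% but < 5 mm above nadir as iSD whatever the change from baseline, contradicting the rest of the appendix and, if applied literally, blocking confirmation of some deep iPR and nodal iCR

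*Protocol*

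**What the plan says.** Phase 3 immune-related response is read from Protocol Appendix F, Tables 15 and 16. For progression, footnote f adds an absolute threshold to the 20% rise: "the tumor burden must also demonstrate an absolute increase of ≥ 5 mm from nadir for iPD". It then says what to record when the relative threshold is met and the absolute one is not: "but tumor burden is increased ≥ 20% from the nadir, response should be recorded as iSD".

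Four other provisions in the same appendix bear on that visit:

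- Table 15 defines iSD as "Neither sufficient shrinkage to qualify for iCR or iPR nor sufficient increase to qualify for iPD".
- Table 15 and the Table 16 rows give iPR for a fall of at least 30% "relative to baseline confirmed by a consecutive assessment at least 4 weeks (28 days) after first documentation".
- Footnote e says that, once non-nodal lesions are gone, "all lymph nodes < 10 mm in short axis would also be iCR even if lymph node measurements prevent 100% tumor burden reduction".
- The text below Table 16 says: "Determination of best overall response is based on changes in total tumor burden from the baseline (nadir, for iPD) tumor assessment".

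SAP Section 6, Table 2, sets the confirmation rule. For complete response, "the iCR will also not be confirmed if there is a subsequent iPR/iSD/iPD at any time prior to the next iCR". For iPR, an iSD or iPD before the next iPR or iCR has the same effect. iCRR is the proportion of subjects whose best response under that table is iCR.

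**The concern.** A 5 mm floor is there to stop a trivial change in a small residual burden from being called progression. Footnote f goes further and fixes the category as iSD. A subject whose burden has fallen by 87% and then moves by 3 mm is still in partial response under Table 15, but is stable disease under the footnote. Because SAP Table 2 lets an intervening iSD cancel confirmation, the label can carry through to best overall response.

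iCRR is the alpha-controlled hypothesis H4. iORR and iDRR come from the same visit responses, and iORR is also one of the two inputs to the non-binding futility look. A tested endpoint should not depend on which of two contradictory sentences a reader applies.

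**Working it through.** **1. When the footnote applies.** Let N be the nadir and B the visit burden. The footnote needs B ≥ 1.2N and B − N < 5 mm. Both are possible only if 0.2N < 5, that is, N < 25 mm. The affected band is 1.2N ≤ B < N + 5: 6 to < 10 mm for N = 5, 12 to < 15 mm for N = 10, 24 to < 25 mm for N = 20, and empty at N = 25. Small nadirs are expected: Appendix F keeps the actual short axis of nodes below 10 mm and assigns 5 mm to target lesions too small to measure. A lesion assigned 5 mm and later measured at 6 mm is exactly 20% up.

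**2. Visit response under each provision.** The burdens are illustrative.

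| Baseline / nadir / visit (mm) | From baseline | From nadir | Table 15, rows, footnote e | Footnote f, literal |
|---|---|---|---|---|
| 100 / 10 / 13 | −87% | +30%, +3 mm | iPR | iSD |
| 100 / 5 / 6 | −94% | +20%, +1 mm | iPR | iSD |
| 100 / 20 / 24 | −76% | +20%, +4 mm | iPR | iSD |
| 100 / 25 / 29 | −71% | +16%, +4 mm | iPR | not reached: iPR |
| Node only, 20 / 6 / 8 | −60% | +33%, +2 mm | iCR | iSD |

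Where the burden is not at least 30% below baseline and iCR is not met, footnote f and Table 15 agree on iSD. The conflict is confined to responders.

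**3. Best response under SAP Table 2** (visits at least 28 days apart).

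| Sequence (mm) | Best response without f | Visits with f | Best response with f |
|---|---|---|---|
| 100 → 10, 13, 13, 13 | iPR | iPR, iSD, iSD, iSD | iSD |
| 100 → 10, 13, 10, 10 | iPR | iPR, iSD, iPR, iPR | iPR, confirmed only at the last pair |
| 100 → 12, 10, 13, 13 | iPR | iPR, iPR, iSD, iSD | iPR |
| Node 20 → 6, 8, 8, 8 | iCR | iCR, iSD, iSD, iSD | iSD |
| Node 20 → 6, 8, 6, 6 | iCR | iCR, iSD, iCR, iCR | iCR, confirmed only at the last pair |
| Node 20 → 6, 6, 8 | iCR | iCR, iCR, iSD | iCR |

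Confirmation is lost only if the rise falls at or before the confirming visit. A response already confirmed is kept, and a lost one can be recovered by two later qualifying visits.

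**4. Which complete responders are exposed.** A percentage rise from a nadir of 0 mm is undefined, and a non-nodal lesion that reappears ends iCR under Table 15 in any case. Only complete responders with residual measured nodes under 10 mm can be caught.

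**5. Endpoints.** iCRR, iORR and iDRR depend on confirmed response; iDOR depends on who is a responder and when response starts. OS and modified RECIST 1.1 PFS do not use this matrix. iPFS is untouched because the visit is not iPD on either reading. iDCR is untouched because iSD counts as control, and SAP Table 2 waives the 84-day requirement for an unconfirmed iCR or iPR.

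**6. Illustration of frequency.** The documents give no scan variability. Assume the difference between two sums, with no true change, is normal with mean 0 and SD s of 1 to 2 mm. For a 10 mm nadir, the chance per scan of landing in the band is Φ(5/s) − Φ(2/s): 0.023 at s = 1 and 0.152 at s = 2. For a single 6 mm node, iCR is at issue only up to 10 mm, so the chance is Φ(4/s) − Φ(1.2/s): 0.115 at s = 1 and 0.25 at s = 2. These are per-scan chances, not a proportion of subjects.

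**The case against.** Footnote f is attached only to the row for a rise of at least 20%. The sentence just below the table makes nadir the reference for progression only, and Table 15 bars iSD where shrinkage qualifies for response. A careful reader taking these together would record iPR or iCR. iCRR is also a central review endpoint, and SAP Section 6 leaves the central review data specifications to a charter that is not among these documents. Much of this stands: the documents do not show that any response has been or will be lost.

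It does not remove the contradiction. The progression row has to be checked against nadir before the baseline rows; otherwise a subject who relapses while still 30% below baseline could never be iPD. A reader following that order arrives at footnote f, which says iSD and does not send the reader back to baseline. Appendix F states no order of checks. If the charter departs from the footnote, the protocol still needs to match it.

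A reader might go further and infer that true responders are being removed, more of them in the arm with more deep responses, and that H4 loses material power. The documents do not support that. It requires literal application, which is unknown, and the share of responders with small nadirs or residual nodes, which is not given.

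**Conclusion.** Footnote f is wrong as written: it contradicts four provisions of its own appendix, and followed literally it gives a wrong best response in the sequences shown. The exposure is narrow: nadir under 25 mm, residual nodes for iCR, and a rise at or before confirmation. The primary endpoints are not touched.

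The number affected cannot be derived. As an illustration only, take an arbitrary 15% proportional loss of iCR in both arms, applied to the protocol's assumed 20% versus 6% with 330 per arm. The rates become 17.0% and 5.1%, and the odds ratio moves from 3.92 to (0.17/0.83)/(0.051/0.949) = 3.81. The standard error is √[(0.17×0.83 + 0.051×0.949)/330] = 0.0240, so z = 0.119/0.0240 ≈ 4.97. Power at two-sided 0.0005, the lowest iCRR level in SAP Table 5, is about 93%, against about 98% with no loss. At 0.00455 it is still about 98%. Even that loss would be modest. The case for correction rests on the contradiction in a tested endpoint, not on a demonstrated bias or power deficit.

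**What to change.** For endpoint classification, reword footnote f to say that a burden at least 20% but less than 5 mm above nadir is not iPD, and that the visit is classified by change from baseline under Table 15, the Table 16 rows and footnote e. State the order once: progression against nadir first, then response against baseline.

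Check that the central review charter says the same. If central review applied the footnote literally, re-derive the affected visits before iCRR is tested, under charter-level agreement because this changes independent-review calls. Diameters alone are not enough: iCR also needs the recorded non-target and new-lesion status.

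Protocol Section 3.1.3.2 has investigators use the same criteria for treatment decisions. The passages must be reconciled there too; this point does not propose which clinical rule should apply.

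The cost is a short wording change in Appendix F and a charter check. If re-derivation is needed, it uses data already recorded, with no new patients.
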